6.2 Preparation/Handling/Storage/Accountability

6.2.1 Acquisition and accountability

For the GNB arm, bupivacaine 0.5% is a commonly used medication in the ED. The participating physician will obtain this medication as they would during typical interventions. Briefly, the participating physician will order the bupivacaine and dexamethasone with specific instructions to nursing to hold and provide the medications (in their commercially available storage vials) to the participating physician. Clinical pharmacists will approve the ordered medications, after which nursing will retrieve the medications from the secured drug rooms (i.e., Omnicell) and directly hand the unopened vials to the participating physician.

For the control arm, the participating physician will order conventional analgesic medications as they normally would, at which time nursing would retrieve the medications and administer them to the patients in accordance with electronic orders.

6.2.2 Formulation, Appearance, Packaging, and Labeling

For the GNB arm, bupivacaine 0.5% is stored in either the Omnicell (immediately available medication storage within the emergency department) or central pharmacy, where it can be sent down to the ED. The medication is stored at room temperature in individually sealed vials. No preparation other than drawing up the medication with a needle and syringe will be necessary, which will be the responsibility of the participating physician administrating the GNB. Vials are single use and clearly labelled. Bupivacaine will be mixed at the bedside with dexamethasone prior to injection. Bupivacaine on formulary is manufactured by Xellia Pharmaceuticals LLC. Dexamethasone 4mg/mL is also available in the ED Omnicell and commonly utilized in emergency patient care. Bupivacaine 0.5% is distributed by Hospira and dexamethasone sodium phosphate 4mg/mL is distributed by Hikma.

6.2.3 Product Storage and Stability

Bupivacaine 0.5% is stored at room temperature (68F to 77F, per manufacturer [drug information sheet](#)) and is relatively stable. Little or no changes in concentration have been observed at four weeks of storage at room temperature.

Dexamethasone phosphate 4 mg/ml is refrigerated (35F-46F) but is stable for 24 hours at 77F. See drug [datasheet](#).

There is a theoretical risk of crystallization when combining certain local anesthetics and dexamethasone. However, this risk is significantly reduced given that we are using bupivacaine as the local anesthetic. Moreover, the formulation of dexamethasone we are using for this study (water soluble dexamethasone sodium phosphate) is compatible with bupivacaine, whereas more lipophilic formulations (dexamethasone palmitate or acetate) have a higher risk of precipitating when mixed with local anesthetics. Nonetheless, the crystals that may be formed are typically less than 10 microns in diameter, which do not pose any clinical risk ([Choi 2021](#)). No published

studies to date have demonstrated adverse clinical effects relating to possible crystallization of dexamethasone and local anesthetics.

6.2.4 Preparation

For the GNB arm, bupivacaine 0.5% is available in single-use vials as a ready-to-use liquid. It will be drawn up with a blunt needle and syringe and requires no special preparation prior to administration. In this case, three separate syringes will be loaded with the appropriate volume 0.5% bupivacaine (weight-based dosing as described above). To each syringe, 1-2 mg of dexamethasone will be added to the bupivacaine (for a total of 4 mg of dexamethasone).

Preparation of medications for the control arm will be prepared and administered to the patient by nursing as per the electronic orders, as is standard of care.

6.3 Measures to Minimize Bias: Randomization and Blinding

Participants will be randomly assigned to either the intervention arm (GNB) or standard-of-care (control) arm using a commercially available random number generator. Patient consent will explicitly state that they will be randomized into either treatment arm. As this is an open-labeled trial, there will be no blinding of intervention to participants, performing physicians, or research assistants.

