4 STUDY PLAN

4.1 Study Design

This is a prospective, open-label, investigator-initiated, convenience-enrollment, randomized-controlled trial comparing the efficacy of the ultrasound-guided three-point GNB versus conventional analgesia of atraumatic knee pain. Patients who present to the ED with atraumatic knee pain will receive plain film radiography of the knee to evaluate for acute fracture or large knee joint effusion. Patients without radiographic evidence of fracture or large knee joint effusion will be eligible for enrollment. Patients for whom there are concerns for infection, including cellulitis or septic arthritis will be excluded. Other exclusion criteria are listed in Section 5.2. We hypothesize that patients who receive a GNB will experience a greater reduction in pain and longer acting analgesia compared to those managed with conventional analgesia.

Patients who present to one of the four primary ED sites within the Penn Medicine health system (HUP, PPMC, PAH, HUP Cedar) will be eligible for inclusion as participants. Research assistants (RAs), who are present in the ED at HUP and PPMC daily, will assist with recruitment at those sites, and potentially eligible patients at PAH and HUP Cedar will be recruited by participating physicians. The study team will review inclusion and exclusion criteria with the RAs prior to the initiation of patient enrollment. Furthermore, an EPIC Haiku notification will be created to alert the study team of any patient who presents to the ED with knee pain. Prior to recruitment, it is assumed that most patients who will become participants will have been offered conventional oral, intravenous, or topical analgesics as part of their normal treatment regimen. If completion and radiologist read of plain film imaging (1) does not show evidence of acute fracture and (2) does not show evidence of a large knee joint effusion, patients will be screened for eligibility by either an RA or the performing physician. Patients with small or moderate sized effusions will be eligible for inclusion if there is no clinical concern for septic arthritis of the knee. Large effusions will be excluded as this may distort the anatomical and sonographic landmarks for performing the GNB. The physician who performs the GNB for participants may not necessarily be the physician who is primarily caring for the patient clinically in the ED.

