Those patients who satisfy all inclusion criteria will be offered enrollment and consented by a participating emergency physician or RA. Upon consenting, patients will be asked to rate their knee pain on the NRS. This initial evaluation is based on the current severity of the pain, regardless of whether patients received any analgesics prior to obtaining radiography. Study will not begin until plain film imaging has been reviewed by a radiologist, at which point patients will be considered for eligibility.

Utilizing a random number generator, patients will be randomized to either the intervention arm (GNB) or the control (conventional analgesia) arm. Within the intervention arm, a three-point GNB will be performed under ultrasound guidance using 80% of ideal body weight (80% of *actual* body weight if BMI is less than 25 kg/m^2) dosing of 0.5% bupivacaine with 4 mg dexamethasone, divided into three separate aliquots (5 mL of 0.5% bupivacaine with 1-2 mg dexamethasone) which will be administered to the SMGN, SLGN, and IMGN. The performing

physician will first identify all landmarks via ultrasound, which include the superomedial and -lateral knee (aligning the probe longitudinally with the femoral condyle) and the inferomedial knee (aligning the probe longitudinally with the tibial condyle). Color doppler will be applied to note any vascular structures within the field of view of injection. The patient will be placed on the cardiopulmonary monitor prior to the GNB. The GNB will be performed via ultrasound guidance in real-time.

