5.5 Strategies for Recruitment and Retention

Patients presenting to the EDs of HUP, PPMC, PAH, or HUP Cedar with knee pain for whom plain film imaging has been obtained will be screened by a member of study team to determine eligibility based on inclusion and exclusion criteria described in sections 5.1 and 5.2. If the patient is eligible, a member of study team will approach the patient to obtain informed consent.

- Target sample size: 17 patients in both the intervention and control treatment arms
- Anticipated accrual rate: 100%
- Anticipated number of sites and in which participants are to be enrolled: 4 clinical sites (EDs of HUP, PPMC, PAH, or HUP Cedar)
- Source of participants: ED patients
- Recruitment venues: ED
- How potential participants will be identified and approached: (1) Potentially eligible patients under the care of a participating physician will be identified and approached

during the usual course of care. (2) Potentially eligible patients who are not under the direct care of a participating physician will be identified by chart screening and direct communication with the primary physician by either participating physicians or research assistants.

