9.2 Sample Size Determination

To determine the number of patients needed in each study arm for sufficient sample size we considered the primary outcome of change in pain levels pre/post treatment as measured by the NRS as this was the largest sample size needed to detect a clinically meaningful effect.

The sample size was loosely based on an RCT by [Shanahan et al. 2023](#), for which the mean change in the visual analog scale (VAS: 0-10 scale) from baseline at 2 weeks was 3.5 (GNB) and 0.7 (sham injection group). Assuming the mean change in NRS pain score pre/post treatment between the GNB and standard analgesia (difference in difference) will be smaller in a shorter period of time, group sample size of 17 (each group) will achieve 80% power to detect a difference in NRS between treatment arms as small as 1.6, with alpha set at 0.05 and standard deviation of differences set at 2.0 using a two-sided two-sample equal-variance t-test with a 5-10% loss to follow-up at the 24 hour mark.

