9.4.5 Planned Interim Analyses

An interim analysis of the primary and secondary endpoints will be conducted after the enrollment of 30 patients, with 15 patients in each arm. This analysis will assess the data collected up to that point to ensure the study's integrity and to make any necessary adjustments based on the findings.

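### Allocation is described only as a random number generator, with no concealed release step, and the interim is tied to a 15/15 split that simple 1:1 allocation would seldom give

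*Protocol*

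**What the plan says.** All references are to the Protocol.

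- **Method of allocation.** Section 6.3 gives "using a commercially available random number generator". Section 4.1 gives "Utilizing a random number generator, patients will be randomized to either the intervention arm (GNB) or the control (conventional analgesia) arm". No allocation ratio, blocking, stratification, list holder or means of releasing the assignment is stated. Section 6.3 also says that participants, performing physicians and research assistants are not blinded.
- **Arm sizes.** Section 5.5: "Target sample size: 17 patients in both the intervention and control treatment arms". Section 9.2: "group sample size of 17 (each group) will achieve 80% power". The synopsis repeats 17 per arm.
- **Interim.** Section 9.4.5 places it "after the enrollment of 30 patients, with 15 patients in each arm" and allows adjustments in the light of the findings. Section 10.1.2 lists efficacy and futility among the grounds for stopping.
- **Who does what.** Section 4.1 says that "potentially eligible patients at PAH and HUP Cedar will be recruited by participating physicians", and that consent is taken by a participating physician or a research assistant. Under section 6.2.2 the participating physician gives the block. Under section 8.1 the performing physician takes the baseline NRS before randomisation. Under section 4.1 the performing physician collects the post-treatment scores overnight.
- **Analysis set.** Section 9.3 includes patients who are enrolled and receive one of the two treatments.

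**The concern.** There are two separate matters.

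**Release of the assignment.** With no blinding, concealment up to the moment of assignment is the main protection against selection. Here enrolment is by convenience, and the person who decides whether to approach a patient may also be the person who treats and scores that patient. If the same person runs the generator, a draw could be repeated, or the patient not taken forward after an unwelcome result. A patient who is drawn but not treated falls outside the section 9.3 analysis set, so such an event need not show in the results. Bias of this kind cannot be repaired by analysis.

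**Balance assumed by the interim.** Section 9.4.5 joins two conditions, 30 enrolled and 15 in each arm. An unrestricted generator seldom satisfies both at once. The team would then have to choose which condition governs, in an open-label trial where the look may lead to changes or to stopping.

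**Working it through.** **Inputs from the Protocol.** 17 per arm, 34 in total (sections 5.5 and 9.2). Interim at 30 with 15 per arm (section 9.4.5). Difference 1.6, SD 2.0, two-sided alpha 0.05, two-sample equal-variance t-test (section 9.2).

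**Assumption.** Independent draws with probability 0.5 per arm. The Protocol does not state this. It is inferred from the equal targets and the absence of any stated restriction.

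**1. The plan's own figure.** Noncentrality at 17/17 is 1.6 / (2.0 × √(1/17 + 1/17)) = 2.33 on 32 df, which gives power 61.9%, not 80%. That shortfall is a separate matter. It is given here only as the baseline for step 4.

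**2. Chance of the stated splits.** P(exact split at N) = C(N, N/2) / 2^N.

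- N = 30: 155,117,520 / 1,073,741,824 = 0.144, so 15/15 is missed in 85.6% of trials.
- N = 34: 2,333,606,220 / 17,179,869,184 = 0.136, so 17/17 is missed in 86.4%.
- Both: 0.144 × C(4,2)/2⁴ = 0.144 × 0.375 = 0.054.

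Larger imbalance at 34, as 2 × P(X ≤ k) with X ~ Binomial(34, 0.5): 14/20 or worse 0.39, 12/22 or worse 0.12.

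**3. If the team waits for 15 in each arm.** Simulation (200,000 runs) gives a mean total of 34.3, with median 33 and 95th percentile 42. The mean is about the whole planned sample. In 39% of trials (14/20 or worse at 34) the smaller arm is still below 15 when all 34 are in. Waiting for 17 in each arm takes 38.6 patients on average, with 95th percentile 47.

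**4. Power cost of imbalance.** Noncentrality is 1.6 / (2.0 × √(1/n₁ + 1/n₂)) on 32 df.

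| Split | Noncentrality | Power |
|---|---|---|
| 17/17 | 2.33 | 61.9% |
| 14/20 | 2.30 | 60.5% |
| 12/22 | 2.23 | 58.0% |
| Average over all splits | – | 60.6% |

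The average loss is 61.9 − 60.6 = 1.3 points.

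**5. What blocking would give.** With one list in blocks of 4, both 30 = 7 × 4 + 2 and 34 = 8 × 4 + 2 stop two patients into a block. The split is then exact with probability 4/6 = 67%, and otherwise 14/16 or 16/18. With block sizes 4 and 6 chosen at random with equal probability (assumed; 200,000 simulated lists), 15/15 at 30 and 17/17 at 34 each occur in about 77% of trials, and both in about 60%. The difference between arms at either point is never more than 2.

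**The case against.** **The premise comes from silence.** The Protocol nowhere says that allocation is unblocked, done at the bedside or done without a list. A generator can produce a permuted-block list, equal targets fit an intended restriction, and block sizes are often kept out of protocols on purpose. The schema and schedule figures are not visible. This stands, so the 14% figures are conditional on simple allocation.

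**A stronger reading is tempting: that the enrolling physician can see the sequence.** The documents do not support it, because no section says so. With independent draws made on the spot there is no sequence to foresee, and the exposure is then a repeated or ignored draw. The supported statement is that no concealment procedure is described.

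**Some safeguards exist.** Consent and the baseline NRS already come before randomisation (sections 4.1 and 8.1). Section 5.4 asks for minimal data on patients who consent but are not randomised or entered. Section 10.1.9 asks the team to document departures from the protocol. This stands in part. The order is stated but nothing enforces it, the drawn arm is not among the section 5.4 items, and section 10.1.9 depends on the staff concerned to declare the event.

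**The interim has a usable trigger.** Section 9.4.5 can be read as 30 patients, with 15 per arm as the nominal split, and no stated boundary depends on exact balance. That reading is fair, so it would be too strong to call the trigger undefined. The wording still leaves two candidate triggers that usually fall at different times under simple allocation.

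**17 per arm is a planning figure.** This is correct. Equal-n power calculations are usual under simple randomisation, and the loss in step 4 is small.

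**Blocking does not guarantee balance and adds some predictability.** This too is correct, and it is why the interim should be reworded whatever method is used.

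**Conclusion.** The point holds as a specific and inexpensive improvement to sections 6.3 and 9.4.5. Allocation is stated only as a random number generator. In an open-label trial with convenience enrolment, one physician may fill every role from recruitment to outcome collection, and no described step conceals the assignment or logs it independently. This is an exposure to selection bias, not evidence that it will occur, and its size cannot be computed from the document.

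The interim wording is a smaller defect. Under simple 1:1 allocation the 30-patient, 15-per-arm condition is met exactly in 14.4% of trials. That figure rests on an allocation method which the Protocol implies but does not state. A reader might infer that imbalance materially weakens the trial. It does not: the average cost is 1.3 points of power, and 3.9 points (61.9 − 58.0) at 12/22.

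**What to change.** **Section 6.3.** State a 1:1 ratio. Have the biostatistician generate one central list with randomly varied permuted blocks, held away from enrolling staff, with the block sizes kept out of the Protocol. Release each assignment through REDCap or an equivalent central system, only after eligibility, consent and baseline NRS have been saved. Log every assignment, including those not followed by treatment.

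**Section 9.4.5.** Define the interim as after 30 randomised patients. Drop the 15-per-arm phrase or mark it as approximate.

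**Cost.** A short set-up and a few sentences of text. The trial already has a biostatistician and uses REDCap, but the Protocol mentions REDCap only for holding and managing data, so the team should confirm that it can also release assignments. Blocks add slight predictability at their ends, which varied sizes and a single list across the four sites limit. Balance improves, but an exact split is still not assured.

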6.4 Study Intervention Compliance

Protocol adherence will require the participant to initially rate their pain on the NRS then to receive either the GNB (intervention arm) or standard-of-care therapy (control arm). At either 1-hour post enrollment or time of discharge from the ED (whichever occurs first), protocol adherence will require the participant to rate their pain on the NRS and complete the APS-POQ-RED questionnaire. At 24 to 36 hours after treatment, participants will be contacted by the performing physician or research assistant to evaluate duration of analgesia received in the ED.

Administration of the trial drugs will be documented (unblinded) in the electronic medical record (PennChart, Epic) as administered medications. These will similarly be documented by the participating physician or research assistant in REDCap. Similarly, medications administered prior to study initiation and medications administered to the control arm and any additional medications administered after treatment will be documented in the electronic medical record (PennChart, Epic) as administered medications as well as in REDCap by the participating physician or a research assistant. Clinical outcome data will be documented in REDCap by the participating physician or a research assistant.

6.5 Concomitant Therapy

For the GNB arm, in addition to bupivacaine, the GNB will be augmented with adjuvant dexamethasone (4 mg divided into three aliquots). Dexamethasone is commonly used in the

perioperative setting by regional anesthesiologists and in the ED to extend the duration of regional anesthesia ([Fernández Martin 2023](#)).

6.5.1 *Rescue Medicine*

For the GNB arm, if signs or symptoms of LAST were to develop at any point during administration of the intervention drug or after administration, patients will be assessed for the need for rescue medications. At all study sites, benzodiazepines and lipid emulsion therapy will be available and administered if deemed necessary by the performing physician ([Shalaby 2024](#)). For seizures, a benzodiazepine such as midazolam or lorazepam will be administered as per established dosing guidelines. Intralipid will be administered as per institutional guidelines to help reverse LAST. The date and time of rescue medication administration as well as the name and dosage regimen of the rescue medication will be recorded.

7 STUDY INTERVENTION DISCONTINUATION AND PARTICIPANT DISCONTINUATION/WITHDRAWAL

7.1 Discontinuation of Study Intervention

The intervention in this study is a one-time three-point GNB performed with bupivacaine and dexamethasone. Moreover, both prior to and after the intervention, patients will continue to receive analgesia as needed in accordance with standard of care (e.g., a patient receives a GNB but still has significant pain 60-minutes afterward will be offered additional conventional analgesics, at the discretion of the primary physician).

7.2 Participant Discontinuation/Withdrawal from the Study

Participants are free to withdraw from participation in the study at any time upon request.

7.3 Lost To Follow-Up

A participant will be considered lost to follow-up if he or she does not respond via telephone at the 24-hour follow-up after three attempts by the participating emergency physician or clinical research assistant. However, patient intervention and any outcome data that has previously been obtained (e.g., data collected at time of discharge from the ED) will still be included. All participants who complete the initial assessment by the time of discharge will be included in the analysis. No follow-up visits will be required.

8 STUDY ASSESSMENT AND PROCEDURES

8.1 Efficacy Assessments

Patients presenting to the ED of one of the four study locations (HUP, PPMC, PAH, HUP Cedar) with knee pain attributed to knee OA with plain film radiography who are eligible for enrollment based on the inclusion and exclusion criteria described in sections 5.1 and 5.2 will be approached by a member of the study team to obtain informed consent.

Prior to randomization, a pain score will be obtained using the NRS by the performing physician. Patients will be randomized to either the intervention arm (GNB) or the control arm, at which point they will receive treatment. At either 1-hour after enrollment or at time of discharge from the ED (whichever occurs first), the performing ED physician, or research assistant will ask the patient to rate their pain severity on the NRS. At that same time, a member of the study team will also have the patient complete the APS-POQ-RED. At 24 to 36-hours after treatment, a clinical research assistant or the treating emergency physician will contact the patient to obtain follow-up assessment and duration of analgesia.

